2. LIST OF ABBREVIATIONS

Abbreviation	Definition
ACR	American College of Rheumatology
AE	Adverse Event
BID	Twice daily
CDAI	Clinical Disease activity index
CRP	C- reactive protein
csDMARD	Conventional Disease modifying anti-rheumatic drug
DAS	Disease activity score
mDAS	Modified Disease Activity Score
EMA	European Medicines Agency
ESR	Erythrocyte sedimentation rate
EQ-5D	Euro Qol 5D
FDA	Food and Drug Administration
GPP	Good Pharmacoepidemiology Practices
GEP	Good Epidemiology Practices
mHAQ	modified Health Assessment questionnaire
HAQ	Health Assessment questionnaire
IEA	International Epidemiology Association
IEC	Independent Ethics Committee
IR	Immediate Release
IRB	Institutional Review Board
ISPE	International Society of Pharmacoepidemiology
JAK	Janus kinase
LDA	Low Disease Activity
LTE	Long Term Extension
MCID	Minimally clinically important difference
MR	Modified release
MTX	methotrexate
NI	Non Interventional
PD	Pharmacodynamic
PK	Pharmacokinetic
PS	Propensity Score
QD	Once daily
RA	Rheumatoid arthritis
SAP	Statistical analysis plan
SAS	Statistical Analysis System
TyK2	Tyrosine kinase 2
US	United States

4. ABSTRACT

Not Applicable.

5. AMENDMENTS AND UPDATES

None.

6. MILESTONES

Milestone	Planned date
Final approved protocol*	December 2019
Start of analysis/data collection	30 September 2018
Approved SAP	20 March 2018
End of data collection	30 August 2019
Final study report	11 October 2019

* This protocol was created retrospective from start of data collection and is part of an Significant Quality Event (SQE).

7. RATIONALE AND BACKGROUND.

Tofacitinib is a potent, selective inhibitor of the Janus kinase (JAK) family of kinases with a high degree of selectivity against other kinases in the human genome. In kinase assays, tofacitinib, inhibits JAK1, JAK2, JAK3, and to a lesser extent tyrosine kinase 2 (TyK2). In cellular settings where JAK kinases signal in pairs, tofacitinib preferentially inhibits signaling by heterodimeric receptors associated with JAK3 and/or JAK1 with functional selectivity over receptors that signal via pairs of JAK2. The efficacy and safety of tofacitinib 5 mg twice daily (BID) administered as monotherapy or in combination with conventional disease modifying anti rheumatic drugs (csDMARDs), mainly methotrexate (MTX), in patients with moderately to severely active rheumatoid arthritis (RA), have been demonstrated in Phase 2,¹⁻⁵ Phase 3,⁶⁻¹¹ and Phase 3b/4¹² studies of up to 24 months' duration, and in long-term extension (LTE) studies with up to 9.5 years of observation.¹³⁻¹⁵

The immediate release (IR) formulation of tofacitinib was approved in November 2012 in the US for the treatment of moderate to severe rheumatoid arthritis (RA) as a twice daily (BID) regimen. It was followed by Food and Drug Administration (FDA) approval of 11 mg modified release once daily (QD) dose in February of 2016.

The modified release (MR) QD regimen has the potential to improve drug compliance of patients, patient convenience, and to offer additional dosing options for patients. Data from completed pharmacokinetic (PK) studies demonstrated that the desired pharmacokinetic and pharmacodynamic (PK-PD) profile was achieved by the MR dose. Overall similarity of PK parameters between IR and MR formulations were found Phase 1 PK studies comparing MR and IR formulations. Therefore, based on the pharmacokinetic (PK) profile for the 2 formulations (IR and MR) and from the information obtained from IR BID programs, FDA approved MR based on clinical pharmacology studies.

It is hypothesized that patients prescribed tofacitinib 11 mg MR formulation once daily (QD) will achieve similar benefit to those prescribed tofacitinib 5 mg BID dosage in real world use. This study will therefore seek to compare the effectiveness of the MR 11 mg QD regimen to the IR 5 mg BID regimen for the treatment of RA in a real-world registry of RA patients.

8. RESEARCH QUESTION AND OBJECTIVES

Primary Objective:

The overall aim of this study is to compare clinical effectiveness of tofacitinib in patients initiating tofacitinib 11 mg QD or 5 mg BID identified from the Corrona US RA Registry.

Secondary Objective:

The study also aims to descriptively assess effectiveness in patients that switched from tofacitinib 5 mg BID to tofacitinib 11 mg QD after February 2016.

9. RESEARCH METHODS

9.1. Study Design

This is an observational study conducted in a cohort of tofacitinib-exposed patients to evaluate effectiveness of tofacitinib MR 11 mg QD tablet compared to IR 5 mg BID tablet. In this secondary data collection study of structured data, patient therapeutic strategies are not determined by this protocol.

9.2. Setting

Using the United States (US) Corrona RA Registry database,¹⁶ patients with RA who have been exposed to tofacitinib IR or MR on or after February 2016 will be included in this study. In order to adequately measure the outcome, the initiators will also be required to have a follow-up visit at 6 months (+/- 3 months) after tofacitinib initiation.

For the primary analysis comparing QD to BID patients, we will consider those patients who initiated tofacitinib 5 mg BID on or after February 2016 and those that initiated tofacitinib 11 mg QD after it became available in February 2016. Although the sample size will be smaller than if all tofacitinib 5 mg BID patients were considered, the inclusion of those patients may introduce noise since there is the possibility that they could differ from the more recent initiators. Therefore, we will consider the cleaner cohort of all patients initiating tofacitinib on or after February 2016.

For the secondary aim, patients that switched from tofacitinib 5 mg BID to tofacitinib 11 mg QD (“switchers”) will be considered. Patients will be considered to have switched from 5 mg BID to 11 mg QD if they initiated 5 mg BID after February 2016 and subsequently changed their dose to 11 mg QD.

9.2.1. Inclusion Criteria

Patients must meet all of the following inclusion criteria to be eligible for inclusion in the study:

1. All US Corrona RA Registry patients who initiated tofacitinib 5 mg BID or tofacitinib 11 mg QD after it became available in February 2016.

2. Patients must have a follow-up visit at 6 months (+/- 3 months) after tofacitinib initiation. These 6 month visits are part of routine practice and is not associated with this protocol.
3. Patients must have a valid clinical disease activity index (CDAI) at initiation and at 6-month follow-up visit.

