### Background:

Tofacitinib (tofa) 11 mg QD was approved in February 2016. It is hypothesized that this formulation will behave similarly to the Tofacitinib 5 mg BID dosage in terms of efficacy.

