### Secondary Outcomes for Overall Aim:

- Change from baseline to 6 month follow-up CDAI (as a continuous variable)
- Achievement of Remission (CDAI $\leq$ 2.8) at 6 month follow-up (among all)
- Achievement of Remission (CDAI $\leq$ 2.8) at 6 month follow-up (among those that were not in remission at initiation)
- Achievement of Low Disease Activity (LDA) (CDAI $\leq$ 10) at 6 month follow-up (among all)
- Achievement of Low Disease Activity (LDA) (CDAI $\leq$ 10) at 6 month follow-up (among those that were not in remission or LDA at initiation)
- Achievement of improvement from baseline to 6 month follow-up in modified HAQ (mHAQ) of 0.25 (as a dichotomous variable)
- Change from baseline to 6 month follow-up modified HAQ (mHAQ as a continuous variable)
- Achievement of improvement from baseline to 6 month follow-up in HAQ of 0.22 (as a dichotomous variable)
- Change from baseline to 6 month follow-up HAQ (HAQ as a continuous variable)
- Change from baseline to 6 month follow-up modified DAS (mDAS as a continuous variable)
- Change from baseline to 6 month follow-up DAS ESR (as a continuous variable)
- Change from baseline to 6 month follow-up DAS CRP (as a continuous variable)
- Change from baseline to 6 month follow-up patient pain (as a continuous variable)
- Change from baseline to 6 month follow-up patient fatigue (as a continuous variable)
- Change from baseline to 6 month follow-up EQ-5D index (as a continuous variable)

- Modified ACR20, ACR50, ACR70

Please see Appendix for more details on the secondary outcomes.

Patients that switched to an agent other than tofa during the 6 months of follow-up will be considered for the continuous outcomes at the time of switch (rather than at 6 months).

In **Tables 2 and 3**, for the dichotomous primary and secondary outcomes, patients that discontinued or switched to an agent other than tofa will be considered as non-responders (e.g. did not achieve remission for patients that discontinued or switched prior to their 6 month visit).

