### Population for Overall Aim:

For the primary analysis comparing QD to BID patients, we will consider those patients who initiated tofa 5 mg BID on or after February 2016 and those that initiated tofa 11 mg QD after it became available in February 2016. Although the sample size will be smaller than if we consider all tofa 5 mg BID patients, the addition of those patients may introduce noise since there is the possibility that they could differ from the more recent initiators. Therefore, we will consider the cleaner cohort of all patients initiating tofa on or after February 2016.

In order to adequately measure the outcome, the initiators will also be required to have a follow-up visit at 6 months (+/- 3 months) after tofacitinib initiation.

The data cut to be used will be the most recent available.

With regards to dosing, patients can be categorized as follows:

QD dosing: once-daily tofacitinib 11mg

BID dosing: 5mg twice-daily

Other: other dosages including 10 mg and will also include not specified

Those in the "other" category will not be considered in these analyses.

The first initial look at the data has indicated that the tofa 5 mg BID group differs on some characteristics from the tofa 11 mg QD group. To account for these differences, in a second look at the data, we propose to consider models adjusted for no more than 10 covariates. This will provide a robust analysis, while preserving sample size. The full propensity score analysis will be done in the final look at the data when the sample size is large enough (as per preliminary power calculations on page 23).

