**Table 2a: Other outcomes of 11 mg QD vs. 5 mg BID Initiators**

*Table generated “after propensity score matching” only for the final analysis.*

	11 mg QD Initiators N=	5 mg BID Initiators N=	p-value*
Other outcomes	Response Rate	Response Rate	
Switching status**			
% Remained on drug at 6 month visit			
% Discontinued initiated drug and did not start another biologic at/before 6 month visit			
% Switched initiated drug to another biologic at/before 6 month visit			

\*P-value will be from a 2 degree of freedom chi-squared test investigating the relationship between the two treatment arms and the 3 switching status categories.

\*\*The “discontinued initiated drug” category will be defined as discontinuation of tofacitinib without a new biologic started. The “switched initiated drug” category was defined as discontinuation of tofacitinib with a new biologic started.

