Analysis: We will update the sample selection figure to reflect the sample derived from the end of September 2018 version of the registry. Reasons for exclusion will be detailed and will include: initiated treatment too late (i.e. after 3/31/2018) and so had not reached time for 6 month visit, no 6 month visit despite having initiated treatment

longer than 6 months ago, no valid CDAI at initiation, and no valid CDAI at 6 months despite attending visit.

	5 mg BID (N/%)	11 mg QD (N/%)
Initiated after 3/31/2018 (not reached 6 months)		
No 6 month visit		
No valid CDAI at initiation		
No valid CDAI at attended 6 month visit		

In addition to the analyses, we will provide an interpretation of the results, including thoughts on the reasons for the listed difference. We will also assess the potential biases that may be introduced into the analyses due to the exclusion criteria.

**Objective 3:** Repeat the primary analyses (Tables 1 – 3\_adj) using a propensity score trimmed population.

To ensure the adjusted analyses do not extrapolate due to the use of dissimilar patients, the propensity score which was previously used to match patients can be used to trim the population of the initiations for which there is no similar initiation in the other group – carrying out the multivariable adjustment for patients on “common support” across the covariates of interest. The propensity score distribution will be examined in both populations and each population will be trimmed for extreme values: patients in one group with propensity scores higher or lower than scores in the other group will be “trimmed” (i.e., excluded from analyses). Only patients with scores overlapping both distributions will be included in the analysis.

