Analyses: The analyses will be updated in the same way as in objective 1, using the propensity score trimmed population instead of the full analysis population. When considering covariates to include in adjusted analyses, we will adjust for age, gender, duration of RA, and baseline CDAI (as in the primary analyses), in addition to any imbalanced covariates (those with standardized difference > 0.2). New analyses will be incorporated into the existing report and tables will be named so as to avoid confusion with pre-existing analyses. We will update Table 2 to include the results of a chisquare test in addition to the original t-test results and we will provide an interpretation of both. Along with each newly analyzed section, we will describe any changes from the previous analyses and we will provide interpretation of all results.

CCI  
[Redacted]

[Redacted]

CCI [Redacted]

[Redacted]

[Redacted]

CCI [Redacted]

[Redacted]

CCI [Redacted]

[Redacted]

CCI [Redacted]

CCI

[Redacted]

CCI

[Redacted]

[Redacted]

[Redacted]

[Redacted]

[Redacted]

CCI

[Redacted]

[Redacted]

CI

CCI

CCI

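### Counting all 296 ineligible initiators as non-responders in both arms is a worst case for each arm's response rate, not for the QD-BID difference

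*Protocol*

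**What the plan says.** Protocol 9.2.1 makes a visit 3 to 9 months after initiation an entry condition ("Patients must have a follow-up visit at 6 months (+/- 3 months) after tofacitinib initiation") and also requires a valid CDAI at initiation and at that visit. Protocol 9.2 and the SAP section Population for Overall Aim repeat the visit condition ("the initiators will also be required to have a follow-up visit at 6 months"). For binary outcomes, the SAP scores patients who stopped or switched as non-responders, with the example "did not achieve remission for patients that discontinued or switched prior to their 6 month visit".

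The later SAP additions respond to the loss of patients:
- Addendum 054c, Objective 2, lists reasons for exclusion by arm and promises: "We will also assess the potential biases that may be introduced into the analyses due to the exclusion criteria".
- Proposed Analyses, item 1, moves to the 2019/08/31 registry version, which leaves 573 of 869 with an eligible visit.
- Proposed Analyses, item 2, adds a table modelled on the full-population Table 2. It includes all 869 initiators and scores those without an eligible visit as not achieving MCID.
- The Justification section describes this as exploring a theoretical worst case for the MCID rate. It also widens the visit window to the first year (689 patients).
- A further section compares eligible with non-eligible initiators on characteristics at initiation.

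The SAP Background states the hypothesis: "It is hypothesized that this formulation will behave similarly to the Tofacitinib 5 mg BID dosage in terms of efficacy". Protocol section 7 says the same for real-world use.

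**The concern.** A sensitivity analysis for missing outcomes should show how far the conclusion could move if the unseen patients differ from those seen. The question here is comparative, and Table 2, the model for the new table, sets the arms side by side with a p-value. Giving the same outcome to the ineligible patients of both arms, when nearly equal shares are ineligible, tests each arm's level. It hardly tests the difference between arms. Where the hypothesis is similarity, a rule that shrinks sizeable differences and adds apparent precision can reassure without having examined the situation that matters, namely ineligible patients faring differently by arm. Protocol section 12 says results may be reported to the EMA in support of the MR submission, so how this table is labelled affects how it will be read.

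**Working it through.** **Inputs.** From the SAP eligibility table (2019/08/31 version):

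| | All | QD | BID |
|---|---|---|---|
| Initiators | 869 | 611 | 258 |
| No follow-up | 113 | 79 | 34 |
| First follow-up after the first year | 67 | 51 | 16 |
| First-year follow-up, no six-month visit | 116 | 80 | 36 |
| Eligible visit | 573 | 401 | 172 |

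The 50% response rate is the planning assumption in Protocol 9.5. The 65% rate adds the 15-point difference named there. Neither is an observed result.

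**Plan's own figure.** 113 + 67 + 116 = 296 = 869 - 573, and 296/869 = 34.1%, which reproduces the 34% in Proposed Analyses. By arm: 210/611 = 34.4% QD and 86/258 = 33.3% BID. The widened-window count also reproduces: 573 + 116 = 689.

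**Effect of the rule on the difference.** With response pQ and pB in the analysed patients and 0% in all ineligible patients:

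D = pQ x 401/611 - pB x 172/258 = 0.656 pQ - 0.667 pB

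| Analysed QD vs BID | Analysed difference | 869-patient difference |
|---|---|---|
| 50% vs 65% | -15.0 | 32.8 - 43.3 = -10.5 |
| 65% vs 50% | +15.0 | 42.7 - 33.3 = +9.3 |
| 50% vs 50% | 0.0 | 32.8 - 33.3 = -0.5 |
| 50.5% vs 50% | +0.5 | -0.2 |

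Rewritten, D = 0.667 (pQ - pB) - 0.010 pQ. A large difference loses about a third. Near zero, the result is a shift of about -0.5 points.

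**Range of the difference.** Let the ineligible respond at q (QD) and b (BID). With 50% in both analysed groups:

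D = (200.5 + 210q)/611 - (86 + 86b)/258

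| q \\ b | 0% | 50% | 100% |
|---|---|---|---|
| 0% | -0.5 | -17.2 | -33.9 |
| 50% | +16.7 | 0.0 | -16.7 |
| 100% | +33.9 | +17.2 | +0.5 |

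The bounds are the opposed corners, -33.9 and +33.9. Their width is 34.4 + 33.3 = 67.7 points at any analysed response rate. The planned analysis is the top-left cell, close to the middle of that range. With 50% vs 65% analysed, the bounds are -43.9 to +23.9 and the planned rule gives -10.5.

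**Tipping points.** Starting from 50% vs 50%, a 15-point QD deficit in the full cohort needs, for example, q = 0% with b = 43%, or q = 25% with b = 69%.

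**Precision.** The 95% half-width at 50% vs 50% in the analysed patients is 1.96 x sqrt(0.25/401 + 0.25/172) = 8.9 points. In the 869-patient table it is 1.96 x sqrt(0.328 x 0.672/611 + 0.333 x 0.667/258) = 6.9 points, giving about -7.4 to +6.3. The interval is narrower because 296 assumed outcomes are counted as data.

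**The case against.** The Justification section speaks of the rate of achieving MCID, not of the difference, and for a rate the label is fair. This stands, and the plan makes no express claim about the difference. But the table follows Table 2, which compares arms, so a reader will use it for the comparison unless told otherwise.

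The plan does much already: newer data, a wider window, a baseline comparison and a promised bias assessment. Exclusion is balanced overall and by row (13% vs 13%, 8% vs 6%, 13% vs 14%). All of this stands. However, equal shares excluded do not show equal outcomes among the excluded, and none of the visible analyses varies those outcomes by arm.

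Three stronger readings are tempting, and the documents do not support them.
- A reader might infer that the visit requirement has biased the comparison. Nothing shows this; it would need outcomes among the ineligible to differ by arm.
- A reader might infer that stopping and switching go unexamined in all 296. Table 2a describes analysed patients ("Discontinued initiated drug and did not start another biologic at/before 6 month visit" is one of its rows). But the 689-patient analysis is to replicate all analyses, so it should carry Table 2a and the non-responder rule to 116 of the 183 ineligible patients with any follow-up. Another 113 have no follow-up to report, which leaves 67 (51 QD, 16 BID). Redacted text nearby may cover these.
- A reader might infer that the rule shrinks every difference by a third. Near zero it does not: +0.5 becomes -0.2, slightly against QD.

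**Conclusion.** The point holds as a limit on what the 869-patient analysis can show. It is the floor for each arm's response rate, apart from the small number with an eligible visit but no valid CDAI, whom the rule as worded does not score. It is not a worst case for the QD-BID difference. At an assumed 50% in both analysed groups it returns -0.5 points within possible bounds of -33.9 to +33.9. It turns an assumed -15.0 into -10.5, and the half-width falls from about 8.9 to 6.9 points. The counts are the SAP's and the response rates are assumptions, but the 67.7-point width does not depend on them. The extremes are bounds, not expectations. For a similarity hypothesis the analysis should not be presented as conservative. The change is worth making; it is not a finding that the primary result is biased.

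**What to change.** Keep the primary population and the 869-patient table, and make these changes:

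1. Describe that table as a worst case for arm-specific response rates only.
2. Beside it, report the QD-BID difference with 95% CI over a grid of response rates among the ineligible, varied separately by arm and including the two opposed extremes. State which combinations would change the conclusion and how the interval treats the assumed rates.
3. As a minor addition to the bias assessment promised in Addendum 054c, Objective 2, tabulate recorded drug status by arm for the 183 ineligible patients with out-of-window follow-up (131 QD, 52 BID). The 689-patient replication should already cover 116 of them.

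Multiple imputation under missing at random is optional. It adds no outcome information for the 113 patients never seen again.

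The cost is one grid, one small table and one reworded sentence, on registry data already held. The drawback is that the bounds are wide and will make a conclusion of similarity look less certain.

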9.2.2. Exclusion Criteria

There are no exclusion criteria for this study.

9.3. Variables

The US Corrona RA Registry is an efficient data collection system for evaluating a range of efficacy outcomes associated with therapies used to treat RA. The endpoints chosen for this study will be extracted from patient and physician questionnaires. Demographic data collected includes age, gender, race and ethnicity. In addition, baseline disease characteristics like disease duration and severity etc. will be captured for both the IR and MR cohorts under study to evaluate disease characteristics.

Primary outcome: Minimally clinically important difference (MCID) improvement as defined by difference in Clinical Disease activity index (CDAI) from initiation to 6 month visit. MCID is dependent on baseline disease activity (at initiation); $MCID \geq 2$ if CDAI at initiation of Low $CDAI \leq 10$, $MCID \geq 6$ if CDAI at initiation Moderate of $10 < CDAI \leq 22$ and $MCID \geq 11$ if CDAI at initiation high of > 22 .

Secondary Outcomes:

- Change in CDAI from baseline to 6 month follow-up (as a continuous variable).
- Achievement of Remission ($CDAI \leq 2.8$) at 6 month follow-up (among all).
- Achievement of Remission ($CDAI \leq 2.8$) at 6 month follow-up (among those that were not in remission at initiation).
- Achievement of Low Disease Activity (LDA) ($CDAI \leq 10$) at 6 month follow-up (among all).
- Achievement of Low Disease Activity (LDA) ($CDAI \leq 10$) at 6 month follow-up (among those that were not in remission or LDA at initiation).
- Achievement of improvement from baseline to 6 month follow-up in modified Health Assessment Questionnaire (mHAQ) of at least 0.25 (as a dichotomous variable).
- Achievement of improvement from baseline to 6 month follow-up in Health assessment questionnaire (HAQ) of at least 0.22.

- Change from baseline to 6 month follow-up HAQ (HAQ as a dichotomous variable).
- Change from baseline to 6 month follow-up modified HAQ (mHAQ as a continuous variable).
- Change from baseline to 6 month follow-up HAQ (HAQ as a continuous variable).
- Change from baseline to 6 month follow-up modified Disease activity Score (mDAS as a continuous variable).
- Change from baseline to 6 month follow-up Disease activity score- erythrocyte sedimentation rate (DAS ESR) (as a continuous variable).
- Change from baseline to 6 month follow-up DAS- C- reactive protein (DAS CRP) (as a continuous variable).
- Change from baseline to 6 month follow-up patient pain (as a continuous variable).
- Change from baseline to 6 month follow-up patient fatigue (as a continuous variable).
- Change from baseline to 6 month follow-up Euro-Qol (EQ-5D) index (as a continuous variable).
- Modified American College of Rheumatology (ACR) ACR20, ACR50, ACR70.

Detailed definitions for the original analysis as well as all subsequent analyses will be included in respective statistical analysis plans (SAPs).

